## **9.6 Safety Analyses**

### **9.6.1 Analyses of Primary Safety Endpoint(s)**

The primary endpoint of this study is safety. The analysis will include the descriptive summary statistics for adverse events, disease-related events, laboratory measures, vital signs, physical measurements. Details are described in respective section below. Safety analysis set will be used for analyses included in this section.

### **9.6.2 Adverse Events**

The Medical Dictionary for Regulatory Activities (MedDRA) version 24.0 or later will be used to code all events categorized as adverse events, all disease-related events to a system organ class and a preferred term. The severity of each adverse event will be graded using CTCAE criteria version 4.03.

Subject incidence of all treatment-emergent, serious treatment-emergent, treatment-related, serious treatment-related, disease-related treatment-emergent, those leading to withdrawal from investigational product, and fatal adverse events will be tabulated by system organ class in alphabetical order, preferred term and grade in descending order of frequency. Subject incidence of treatment-emergent adverse events identified by

COVID-19 standardized MedDRA queries and serious adverse events occurring on or after the COVID-19 infection will also be summarized.

Subject incidence of treatment-emergent events of interest (standardized MedDRA queries and/or Amgen Medical Queries) will also be summarized according to their categories, preferred term, and worst severity grade. Events of interest could include but are not limited to Hypersensitivity, Tachyarrhythmias, Tachypnea, Hematopoietic Cytopenia, Drug Reaction with Eosinophilia, Leucocyte Changes, Infection and Infestation, Cytokine Release Syndrome, and Injection Site Reaction. Number of episodes and duration of treatment-emergent injection site reactions will be further summarized by treatment group.

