Five dose cohorts are planned (cohort 1: [REDACTED] μ g [REDACTED] cohort 2: [REDACTED] μ g [REDACTED] cohort 3: [REDACTED] μ g [REDACTED] cohort 4: [REDACTED] μ g [REDACTED] and cohort 5: [REDACTED] μ g [REDACTED]

Procedures

Written informed consent must be obtained from all subjects before any study-specific screening procedures are performed. The following procedures will occur per the schedule of activities: medical and medication history, physical examination, physical measures, vital signs, electrocardiograms, prior and concomitant medication assessment, tuberculosis testing, urinalysis, and blood draw for serum chemistry, hematology, hepatitis B and C testing, human immunodeficiency virus testing, PK/PD, anti-AMG 592 antibodies, biomarker development and pharmacogenetics sample. Women of childbearing potential will have pregnancy tests performed at screening and at regular intervals during the study. Safety assessments including adverse events,

serious adverse events, and disease-related events, will be performed throughout the safety follow-up.

For a full list of study procedures, including the timing of each procedure, please refer to [Section 9.2](#) and the Schedule of Activities in [Table 2-1](#) and [Table 2-2](#).

Statistical Considerations

Descriptive statistics will be provided for selected demographics, safety, PK, PD, **immunogenicity, and** biomarker data. Descriptive statistics on continuous measurements will include means, medians, Q1, Q3, standard deviations, and ranges, while categorical data will be summarized using frequency counts and percentages. Data will be presented and summarized by treatment and also by time as appropriate.

Subject incidence of all treatment-emergent adverse events will be tabulated by system organ class and preferred term. **Subject incidence** of fatal adverse events, serious adverse events, adverse events leading to withdrawal from investigational product or other protocol-required therapies, and significant treatment emergent adverse events will also be provided. Subject incidence of disease-related events, and fatal disease-related events, if applicable, will be tabulated by system organ class and preferred term.

The analyses of safety laboratory endpoints will include summary statistics at selected time points by treatment group. Shifts in grades of safety laboratory values between the baseline and the worst on-study value will be tabulated.

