10.3.2.3.2 Adverse Events and Disease-related Events

Subject incidence of all treatment-emergent adverse events will be tabulated by system organ class and preferred term. Tables of fatal adverse events, serious adverse events, adverse events leading to withdrawal from investigational product or other protocol-required therapies, and significant treatment emergent adverse events will also be provided. Subject incidence of disease-related events, fatal disease-related events, and device-related events, if applicable, will be tabulated by system organ class and preferred term.

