The investigator will then record all relevant adverse event/disease-related event/serious adverse event information in the Event case report form (CRF).

- Additionally, the investigator is required to report a fatal disease-related event on the Event CRF.

The investigator must assign the following adverse event attributes:

- Adverse event diagnosis or syndrome(s), if known (if not known, signs or symptoms);
- Dates of onset and resolution (if resolved);
- Severity (or toxicity defined below);
- Assessment of relatedness to investigational product, other protocol-required therapies; and
- Action taken.

If the severity of an adverse event changes from the date of onset to the date of resolution, record as a single event with the worst severity on the Event CRF.

It is not acceptable for the investigator to send photocopies of the subject's medical records to sponsor in lieu of completion of the Event CRF page.

If specifically requested, the investigator may need to provide additional follow-up information, such as discharge summaries, medical records, or extracts from the medical records. In this case, all subject identifiers, with the exception of the subject number, will be blinded on the copies of the medical records before submission to Amgen.

The investigator will attempt to establish a diagnosis of the event based on signs, symptoms, and/or other clinical information. In such cases, the diagnosis (not the individual signs/symptoms) will be documented as the adverse event/serious adverse event.

Evaluating Adverse Events and Serious Adverse Events

Assessment of Severity

The investigator will make an assessment of severity for each adverse event and serious adverse event reported during the study. The assessment of severity will be based on:

The Common Terminology Criteria for Adverse Events (CTCAE), version 4.03 which is available at the following location:

http://ctep.cancer.gov/protocolDevelopment/electronic_applications/ctc.htm.

Approved

Assessment of Causality

The investigator is obligated to assess the relationship between investigational product, protocol-required therapies, and/or study-mandated procedure and each occurrence of each adverse event/serious adverse event.

Relatedness means that there are facts or reasons to support a relationship between investigational product and the event.

The investigator will use clinical judgment to determine the relationship.

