### **Disease-related Event**

Disease-related events are events (serious or non-serious) anticipated to occur in the study population due to the underlying disease. All serious disease-related events will be recorded and reported to the sponsor or designee within 24 hours. The investigator will submit any updated serious disease-related event data to the sponsor within 24 hours of it being available.

Disease-related events that would qualify as an adverse event or serious adverse event:

An event based on the underlying disease that is worse than expected as assessed by the investigator for the subject's condition or if the investigator believes there is a causal relationship between the investigational product(s)/study treatment/protocol-required therapies and disease worsening, this must be reported as an adverse event or serious adverse event.

Disease-related events that do not qualify as adverse events or serious adverse events:

An event which is part of the normal course of disease under study (e.g., disease progression in oncology or hospitalization due to disease progression) is to be reported as a disease-related event.

Disease-related events pre-defined for this study include: lupus-related joint pain, joint stiffness, joint swelling, rash, alopecia, and mucosal ulcers.

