#### **10.            Changes From Protocol-specified Analyses**

There are no changes to the protocol-specified analyses.

---

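### The SAP does not name the protocol's conditional table of fatal disease-related events, and no planned table shows which disease-related events were serious

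*SAP*

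**What the plan says.** The protocol states the planned table twice. Section 10.3.2.3.2 says: "Subject incidence of disease-related events, fatal disease-related events, and device-related events, if applicable, will be tabulated by system organ class and preferred term". The synopsis says: "Subject incidence of disease-related events, and fatal disease-related events, if applicable, will be tabulated by system organ class and preferred term". Both make it conditional on such events occurring.

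SAP 9.6.2 gives the list of event tables that will be produced. The relevant part reads "disease-related treatment-emergent, those leading to withdrawal from investigational product, and fatal adverse events will be tabulated by system organ class", followed by preferred term and grade. The list includes one disease-related treatment-emergent table. In it, serious qualifies treatment-emergent and treatment-related events, and fatal qualifies adverse events. It names no fatal and no serious disease-related table. SAP 10 says: "There are no changes to the protocol-specified analyses".

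The definitions are in SAP 5.4, which repeats Protocol Appendix 4. It says: "Disease-related events are events (serious or non-serious) anticipated to occur in the study population due to the underlying disease". It then sets apart a class headed "Disease-related events that do not qualify as adverse events or serious adverse events" and describes it as "An event which is part of the normal course of disease under study", with hospitalization for disease progression among its examples. Events that are worse than expected, or thought to be caused by treatment, must instead be reported as adverse or serious adverse events.

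On collection, Protocol Appendix 4 says: "Additionally, the investigator is required to report a fatal disease-related event on the Event CRF". Protocol 9.2.3.1.1.1 requires serious disease-related events to reach the sponsor within 24 hours.

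**The concern.** Safety is the primary endpoint, and SAP 9.6.1 puts disease-related events inside the primary safety analysis. Readers of the study report will go first to the tables of serious and fatal events. If those tables are built strictly from adverse events, a serious or fatal event that the investigator kept in the disease-related category is not in them. Whether it is kept there depends on a judgment about expectedness and causality.

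A randomized comparison by arm is most useful where individual causality judgments are uncertain, as they are for lupus activity under a drug that acts on immune regulation. The protocol's fatal table would partly meet this need. The SAP drops it without saying so.

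**Working it through.** The plan gives no figure on this point, so the check is a comparison of texts. Its only computed figures are the sample-size probabilities, and nothing here depends on them. They do reproduce from 1 − (1 − p)^n:

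- n = 5: 0.7627 at p = 25% and 0.6723 at p = 20% (stated 76% and 67%)
- n = 21: 0.1903 at p = 1% and 0.6594 at p = 5% (stated 19% and 66%)

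**Step 1: planned tables side by side.**

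| Display | Protocol (synopsis, 10.3.2.3.2) | SAP 9.6.2 |
|---|---|---|
| All disease-related events | Yes | Yes, treatment-emergent, with grade |
| Fatal disease-related events | Yes, if applicable | Not named |
| Serious disease-related events | Not named | Not named |
| Serious adverse events | Yes | Yes |
| Fatal adverse events | Yes | Yes |

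The second row is a difference between the documents that SAP 10 does not declare. The third row is a gap in both.

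**Step 2: route of a serious disease-related event under the definitions.**

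1. If it is judged worse than expected or related to treatment, Protocol 9.2.3.1.1.1, Appendix 4 and SAP 5.4 send it to the serious adverse event category. It is then in the serious table, and in the fatal table if fatal.
2. If it is judged to be in the normal course of disease, it stays a disease-related event and is not an adverse or serious adverse event. SAP 5.4 defines a treatment-emergent adverse event as a kind of adverse event, so the serious treatment-emergent and fatal adverse event tables do not take it in.

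**Step 3: where an event on route 2 would be seen.** It is counted in the overall disease-related table by system organ class, preferred term and grade. Grade does not identify seriousness: Protocol 9.2.3.1.1.3 says the CTCAE grade 4 criteria differ from the regulatory criteria for a serious event. The grading sentence in SAP 9.6.2 also mentions adverse events only, so grading of disease-related events is not assured. A death would appear in the disposition summary of SAP 9.2, because Protocol 8.1 and 8.2.2 list it as a reason for removal, but that summary does not link it to a disease-related event.

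**Step 4: scale, as illustration only.** SAP 3.2 plans 5 subjects on AMG 592 in each of cohorts 1 to 3 and 3 in each of cohorts 4 and 5. One such event would be 1/5 = 20% or 1/3 = 33% of a cohort's active subjects. If that cohort had no other serious event, its serious table would show 0/5 or 0/3. These figures show how much one event weighs in a small cohort. They are not expected rates.

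**The case against.** The case against giving this much weight is substantial, and most of it stands.

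- **The omitted table is conditional.** The protocol asks for it only if applicable. The pre-defined disease-related events are joint pain, stiffness and swelling, rash, alopecia and mucosal ulcers, so a death kept in this category is remote. This stands. However, the condition decides whether the table has content, and the SAP provides no table even if the condition is met.
- **The flare scenario is narrow.** A reader might infer that any lupus admission on AMG 592 would be missing from the serious table. The documents do not support that. Events judged related or worse than expected go to the serious adverse event category by rule, and an admission for rash or joint pain could well be judged worse than expected. Renal, neurological and hematological flares are not among the pre-defined events, although the list is introduced as inclusive and may not be closed. The hospitalization example sits beside an oncology example and looks like template text, but it is in force as written.
- **Nothing is lost from the report.** A reader might infer that such events vanish. They do not: the overall disease-related table counts them by grade, and the disposition summary shows deaths. Disease flare needing treatment that the protocol does not allow is also a listed reason for stopping product.
- **The SAP wording is loose.** SAP 9.6.2 lists the disease-related table in a series that ends in adverse events, so a programmer might include disease-related events in the serious and fatal tables. SAP 5.4 points the other way. That ambiguity is itself a reason to state the rule.
- **A serious disease-related table was never promised.** This is correct. Its absence is not a departure from the protocol, and the request for it rests on its merits.

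**Conclusion.** The point holds in a limited form. One protocol-specified, conditional analysis is not named in the SAP, and SAP 10 wrongly says that nothing changed. Separately, neither document plans a display of which disease-related events were serious, although the sponsor receives those events on an expedited basis. Followed exactly, the SAP would leave serious or fatal events judged to be normal-course lupus out of its serious and fatal tables. They would be visible only in the overall disease-related table, where seriousness is not shown, with deaths also listed as discontinuation reasons.

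This conclusion assumes that SAP 5.4 governs how the tables in 9.6.2 are built, and that at least one event stays in the disease-related category because the investigator judged it neither worse than expected nor related. Few such events are likely. The documents give no rate, so the size of any undercount cannot be stated. The cohort fractions above should not be read as an estimate of it. It is a modest reporting gap on the primary safety endpoint, worth closing because that is easy.

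**What to change.** In SAP 9.6.2:

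1. Restore the protocol's subject-incidence table of fatal disease-related events, to be produced if any occur.
2. Add, by treatment group, either the subject incidence of serious disease-related events or one combined line for any serious event, covering adverse and disease-related events together.

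If the fatal table is being dropped deliberately, record that and the reason in SAP 10.

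The cost is a few sentences of SAP wording and one or two short tables. The events are already recorded on the Event CRF, and the serious ones are already reported to the sponsor. Data collection, conduct and sample size do not change.

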#### **9.6.3         Laboratory Test Results**

**The laboratory analytes listed below in the [Table 9-1](#) will be analyzed.** Unscheduled assessments ([Appendix B](#)) will be incorporated in the laboratory analyses where possible.

**For chemistry and hematology lab analytes,** the analyses of safety laboratory endpoints will include summary statistics of baseline, post-baseline values at all time points, change from baseline to post-baseline values at all time points, post-baseline maximum/minimum and change from baseline to post-baseline maximum/minimum by treatment group. Shifts in grades of safety laboratory values between the baseline and the worst on-study value will be tabulated **based on CTCAE version 4.03.** **Subject incidence of worst post-baseline level of eosinophils counts by the laboratory normal range will be tabulated by treatment group.**

**The urine protein analyte in the urinalysis will be graded in the following manner: Negative, Trace, 1+, 2+, 3+, 4+. The number and percent of subjects in these categories at all time points will be presented.**

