Within each cohort subjects will be randomized to AMG 592 or placebo in a 5:2 ratio (cohorts 1, 2, and 3) or in a 3:1 ratio (cohorts 4 and 5). It is planned that approximately 29 subjects will be randomized, with 21 subjects randomized to AMG 592, and 8 subjects randomized to placebo. The total sample size may exceed 29 subjects and the number of subjects per cohort may exceed the planned cohort size if, following a DLRM recommendation or Amgen decision to evaluate additional doses (or further evaluate currently planned doses), dosing cohorts are added and/or existing cohorts are expanded, or subjects are replaced as per [Section 5.2.1](#). Additional subjects may be

Approved

enrolled in each cohort (following originally planned randomization ratio) to enable all screened eligible subjects to participate in the study.

Summary of Subject Eligibility Criteria

Subjects must be adults with SLE according to the Systemic Lupus International Collaborating Clinics (SLICC criteria) or by at least 4 of the 11 criteria of the 1997 American College of Rheumatology (ACR) classification criteria for SLE, with a history of at least one of the following: antinuclear antibody $\geq 1:80$; or elevated anti-dsDNA antibodies. Subjects must be on a SLE treatment for ≥ 12 weeks, may be taking ≤ 3 SLE treatments, and have a stable dose for ≥ 4 weeks prior to day 1. Subjects must have a prednisone dose ≤ 20 mg daily (or other equivalent OCS) with stable dose ≥ 2 weeks prior to day 1. Subjects must be free of infections and significant concurrent medical conditions and laboratory abnormalities including a negative test for tuberculosis, hepatitis B and C, human immunodeficiency virus, and urine drug and alcohol. Women of childbearing potential must have a negative pregnancy test at screening and baseline and must agree to use a highly effective method of birth control.

For a full list of eligibility criteria, please refer to [Section 6.1](#) to [Section 6.2](#).

Treatments

AMG 592 and placebo will be manufactured and packaged by Amgen Inc. and distributed using Amgen clinical study drug distribution procedures. Both are liquid formulations presented in highly similar glass vials and stored in the same manner. AMG 592 or placebo will be administered by SC injection [REDACTED].

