221 Administration of herbal supplements, vitamins, or nutritional supplements within 30 days prior to the first dose of investigational product, and continuing use, if applicable, will be reviewed by the Investigator and the Amgen Medical Monitor to determine acceptability. Written documentation of this review and Amgen acknowledgment is required for subject participation.

Prior/Concurrent Clinical Study Experience

222 Currently receiving treatment in another investigational device or drug study, or less than 30 days at day 1 since ending treatment on another investigational device or drug study(ies). Other investigational procedures while participating in this study are excluded.

223 Subject previously enrolled in this study may not be re-enrolled *unless* they fulfill the following criteria:

- Have completed the study previously without any adverse events deemed related to study drug.
- Have received the last dose of AMG 592/placebo > 6 months prior to the screening visit.
- Must not have tested positive for neutralizing antibodies against AMG 592 at any time.

Diagnostic Assessments

224 Presence of laboratory abnormalities at screening including the following:

- Aspartate aminotransferase (AST) or alanine aminotransferase (ALT) > 1.5 x upper limit of normal (ULN).
- Serum total bilirubin (TBL) \geq 1.5 mg/dL (\geq 26 μ mol/L)
- Hemoglobin < 9.0 g/dL (< 90 g/L)
- Platelet count < 100,000/mm³ (100 x 10⁹/L)
- White blood cell count < 2,000 cells/mm³ (2.0 x 10⁹/L)
- Absolute neutrophil count (ANC) < 1,000/mm³ (1.0 x 10⁹/L)
- Calculated glomerular filtration rate of \leq 50 mL/min/1.73 m² using the Modification of Diet in Renal Disease (MDRD) formula.

225 Any other laboratory abnormality, which, in the opinion of the investigator, poses a safety risk, will prevent the subject from completing the study, will interfere with the interpretation of the study results, or might cause the study to be detrimental to the subject.

Other Exclusions

226 Female subject is pregnant or breastfeeding or planning to become pregnant or breastfeed during treatment and for an additional 6 weeks after the last dose of investigational product.

227 Females of child-bearing potential with a positive pregnancy test (assessed by a serum pregnancy test at screening and a urine pregnancy test at baseline).

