## **5.2 Study Points of Reference**

### **Baseline**

For any variable, baseline is the last assessment taken prior to or on the first investigational product administration unless stated otherwise; for subjects who did not receive any investigational product, baseline is the last assessment on or before enrollment date.

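### The eosinophil table classifies subjects by worst post-baseline level alone, so it cannot separate new elevations from those already present at baseline

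*SAP*

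**What the plan says.** **The table.** SAP 9.6.3 gives eosinophils an output of their own: "Subject incidence of worst post-baseline level of eosinophils counts by the laboratory normal range will be tabulated by treatment group". There is no baseline row or column and no restriction to subjects within range at baseline. The direction of 'worst' is not stated.

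**The neighbouring outputs in SAP 9.6.3.** The sentence before it does use baseline: "Shifts in grades of safety laboratory values between the baseline and the worst on-study value will be tabulated". Those shifts are in CTCAE version 4.03 grades, not in categories of the normal range, and the text does not say whether eosinophils are graded. Chemistry and hematology analytes, which include eosinophils under the white cell differential in Table 9-1, also get summary statistics of baseline, of each time point and of change, ending with "post-baseline maximum/minimum and change from baseline to post-baseline maximum/minimum by treatment group". The current section plans no individual laboratory listing.

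**Entry.** Criterion 224 in Protocol 6.2 opens "Presence of laboratory abnormalities at screening including the following" and names AST/ALT, bilirubin, hemoglobin, platelets, white cells, neutrophils and glomerular filtration rate. Eosinophils are not among them. Criterion 225 leaves any other abnormality to the investigator's opinion.

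**Baseline.** SAP 5.2 provides the value needed: "For any variable, baseline is the last assessment taken prior to or on the first investigational product administration unless stated otherwise". Protocol Table 2-1 schedules hematology at screening and on day -1.

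**Relevance.** SAP 9.6.2 lists possible events of interest that include "Drug Reaction with Eosinophilia, Leucocyte Changes".

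**The concern.** An incidence table by normal range is read to see how many subjects went high on drug. This one shows how many were high at some point after dosing, whatever their count beforehand. The primary endpoint in SAP 2.1 speaks of clinically significant changes in laboratory safety tests. A worst level without a starting level is not a change.

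The arms are very small, so one subject with a long-standing raised count can produce an apparent difference between doses, or hide one. The synopsis says the study's information will be used to determine the recommended phase 2 dose(s), and an eosinophil-related reaction is among the possible events of interest. A reader weighing that question is likely to turn to this table.

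**Working it through.** **Inputs**
- Group sizes, from the protocol synopsis: "with 21 subjects randomized to AMG 592, and 8 subjects randomized to placebo". By cohort (Protocol 10.1), AMG 592 has 5+5+5+3+3 = 21 and placebo 2+2+2+1+1 = 8.
- Baseline prevalence of raised eosinophils (b): not in the documents. I assume 5%, 10% and 20%.
- The SAP says by treatment group. The figures for n=5 and n=3 apply if doses are shown separately; those for 21 and 8 apply to pooled groups.

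**Step 1. Check the formula on the plan's own figures.** SAP 3.2 uses the chance of at least one event, 1 − (1 − p)^n.
- n=5, p=0.25: 1 − 0.75^5 = 0.763 (plan: 76%)
- n=5, p=0.20: 1 − 0.80^5 = 0.672 (plan: 67%)
- n=21, p=0.01: 1 − 0.99^21 = 0.190 (plan: 19%)
- n=21, p=0.05: 1 − 0.95^21 = 0.659 (plan: 66%)

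All four reproduce.

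**Step 2. Weight of one subject who is raised at baseline and again after dosing (1/n).**
- n=3: 33 points
- n=5: 20 points
- pooled placebo, n=8: 12.5 points
- all AMG 592, n=21: 4.8 points

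**Step 3. Chance that a group contains at least one baseline-raised subject, 1 − (1 − b)^n.**

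| b (assumed) | n=3 | n=5 | n=8 | n=21 |
|---|---|---|---|---|
| 5% | 14% | 23% | 34% | 66% |
| 10% | 27% | 41% | 57% | 89% |
| 20% | 49% | 67% | 83% | 99% |

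These are chances of a raised baseline. The table is affected only if a post-baseline value is raised as well. Hematology has ten post-baseline analysis windows in SAP Appendix B, and one raised value is enough.

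**Step 4. Illustration of the mixing.** Assume that every raised baseline persists and that 10% of subjects normal at baseline become high. The table then shows b + (1 − b) × 0.10 as high, of which only (1 − b) × 0.10 is new.
- b=5%: 14.5% shown, 9.5% new; 34% of those shown were high at entry
- b=10%: 19% shown, 9% new; 53% were high at entry
- b=20%: 28% shown, 8% new; 71% were high at entry

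Both the persistence and the 10% onset rate are assumptions chosen to show the mechanism.

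**The case against.** **Other outputs carry baseline information.** SAP 9.1 specifies means, medians, quartiles, standard deviations, standard errors and ranges, and SAP 9.6.3 applies summary statistics to baseline and to change. If results are shown by dose, the minimum, median and maximum are all the values in an arm of 3. In an arm of 5, the five-number summary is all the values under usual quartile definitions. A raised baseline could therefore be seen in just the arms where it matters most. This stands and lowers the stakes. It does not close the gap: the summaries do not show whether the subject with the raised baseline is the one later counted as high.

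**The event-of-interest summary is already treatment-emergent.** Under SAP 5.4 an event must start or worsen on or after first dose, and Protocol 9.2.4 has the investigator judge abnormal values against the subject's own baseline. This also stands. A reader might infer that the reporting of eosinophil-related adverse events is contaminated in the same way; the documents do not support that. SAP 9.6.2 also lists the category only as one that could be included.

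**Stronger readings of the table itself.** A reader might infer that every subject who enters high will be counted as high whatever happens on study. That is wrong, because a post-baseline value must also be above range. Nor does the SAP call the output treatment-emergent or on-treatment eosinophilia; it describes a post-baseline level.

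**Criterion 225 and placebo.** Criterion 225 allows an investigator to exclude a subject for a raised count, but this is discretionary. Randomised placebo offers a comparison, but with 8 subjects one raised baseline is 12.5 points.

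**No stated decision rests on the table.** SAP 2.2 plans no formal hypothesis, and under SAP 7.1 the dose level review meetings work from subject-level laboratory listings and plots. It cannot be inferred that escalation would be misdirected by this output.

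**Conclusion.** The point holds as a modest defect in one descriptive safety table. As specified, the table pools subjects raised before and after dosing with subjects newly raised, and no other final-analysis output in SAP 9.6.3 clearly separates them. The grade-shift table would help only if eosinophils are graded, which is not stated.

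The per-subject weights (20, 33, 12.5 and 4.8 points) follow from the planned group sizes alone. The probabilities and the 34% to 71% share rest on assumed prevalence, and the share also on assumed persistence and onset. They show that the problem is plausible at these sizes, not that it will occur. The consequence is for interpretation only: no test, sample-size figure or stated dosing rule changes.

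**What to change.** In SAP 9.6.3, replace the eosinophil sentence with a specification along these lines:

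- By treatment group, cross-tabulate baseline category (low, normal, high, missing) against worst post-baseline category, using the laboratory normal range.
- State that 'worst' means the highest post-baseline value.
- Report the number and percentage newly high, with subjects known not to be high at baseline as the denominator.

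This extends the baseline-to-worst principle already applied to graded analytes. It needs no new data, since baseline is defined in SAP 5.2 and hematology is drawn at screening and on day -1. The cost is a change to one sentence and a slightly larger table, many of whose cells will be sparse or empty at these group sizes.
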